8.7 Analyses

8.7.1 Primary and Secondary Safety Analyses of the Primary Safety Endpoints

To evaluate the safety and tolerability of RAL through 6 weeks of life, descriptive statistics will be calculated summarizing the safety data from study entry through 6 weeks of life from all safety evaluable infants in the four study groups: (i) Cohort 1 RAL-naïve, (ii) Cohort 1 RAL-exposed, (iii) Cohort 2 RAL-naïve, and (iv) Cohort 2 RAL-exposed infants. Overall summary statistics for the cohort will be provided if the data suggests that there is no difference between RAL-naïve and RAL-exposed infants within that cohort. The primary safety analysis will be the calculation of the point and 2-sided 90% confidence interval (CI) using the Clopper-Pearson exact method estimates of the proportion of infants meeting the primary toxicity endpoint of adverse event Grade 3 or 4 severity or death. Secondary safety analyses will include point and 90% CI estimates of infants with a SADR of Grade 3 or 4 severity or death. Table 14 shows the precision with which confidence intervals around proportions of serious adverse events can be estimated, for the 12 participants in Cohort 1 and for the 8 and 20 participants in the interim and final analyses for Cohort 2.

Table 14
90% Confidence Intervals Around Potential Proportions
of Infants Meeting a toxicity Endpoint^a

Number of participants	Proportion of participants meeting toxicity endpoint	Clopper-Pearson 90% CI
8	0.00	(0.00, 0.37)
	0.25	(0.03, 0.65)
	0.50	(0.16, 0.84)
12	0.00	(0.00, 0.26)
	0.25	(0.05, 0.57)
	0.50	(0.21, 0.79)
20	0.00	(0.00, 0.17)
	0.10	(0.01, 0.32)
	0.20	(0.06, 0.44)
	0.50	(0.27, 0.73)

^a Clopper-Pearson exact confidence interval estimates using SAS Version 9.2.

The primary safety analyses population will include all infants who have had at least one dose of raltegravir. For Cohort 2 RAL-naïve group, if there was dose adjustment after the interim analysis, a sensitivity analysis will be performed on infants who were enrolled after dose adjustment and only took the adjusted dose. Patients who had an idiosyncratic dose adjustment, based on extreme PK data, will be included in the primary analysis.

However, this adjustment will be acknowledged in the narrative part of the report where these results are described.

8.711 Secondary Analyses

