secondary safety endpoints for final analysis)

Note: Summary tables will include statistics for infant subgroups and overall and listing will include information on infant in utero RAL exposure and RAL dosing.

Table: Summary tables showing number (%) and the 2-sided 90% confidence interval (CI) using the Clopper-Pearson exact method estimates of the proportion of infants meeting the primary and secondary safety endpoints(will provide as footnote number of infants with missing data). The primary analysis will be on the primary safety endpoint.

Table 6: Proportion of Infants Meeting the Primary Safety Endpoint (mock-up table)

RAL-naïve			RAL-exposed	Overall
3mg/kg-3mg/kg	2mg/kg- 3mg/kg	Overall	1.5mg/kg-3mg/kg	
N (%) [90% CI]	N (%) [90% CI]	N (%) [90% CI]	N (%) [90% CI]	N (%) [90% CI]

Note: Similar table will be generated for Cohort 2 with appropriate column labels appropriate for Cohort 2 subgroups of infants.

Table: Summary tables of worst adverse events (laboratory, signs/symptoms and diagnoses) for each of the primary and secondary safety endpoint.

Table: Summary of worst grade baseline events (laboratory, signs/symptoms and diagnoses).

Table: Listing of reasons for infant death and age (weeks) at death.

Table: Summary table showing number (%) and the 2-sided 90% confidence interval (CI) using the Clopper-Pearson exact method estimates of the proportion of infants who had total bilirubin exceeding 16.0 mg/dL, or received phototherapy, transfusion therapy or other therapies for hyperbilirubinemia.

The following SDAC internal listings will be generated to facilitate the write-up of the SDAC final report. The listings will also be provided to the manuscript writing team. SDAC public IDs will be used and no identifying dates will be provided.

- a. Per infant listings of baseline events, AEs and SADRs with site and team assessment of drug attribution.
- b. Per infant listing of ARVs from TXW0276 and PE0421.

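### Table 14 is labelled as 90% Clopper-Pearson intervals, but all ten intervals printed in it are 95% intervals

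*Protocol*

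**What the plan says.** Protocol 8.7.1 defines the analysis: "The primary safety analysis will be the calculation of the point and 2-sided 90% confidence interval (CI) using the Clopper-Pearson exact method". The proportion is that of infants with a Grade 3 or 4 adverse event or death through 6 weeks of life. The same section offers Table 14 as the precision available "for the 12 participants in Cohort 1 and for the 8 and 20 participants in the interim and final analyses for Cohort 2". The table title reads "90% Confidence Intervals Around Potential Proportions", its interval column is headed "Clopper-Pearson 90% CI", and its footnote gives the method as "Clopper-Pearson exact confidence interval estimates using SAS Version 9.2".

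SAP 4.6 sets the same level for the final reports: "2-sided 90% confidence interval (CI) using the Clopper-Pearson exact method estimates of the proportion of infants meeting the primary and secondary safety endpoints". Its mock-up Table 6 puts a 90% CI in every cell. Neither document says that Table 14 was computed at any other level.

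**The concern.** With no events in n infants, the two-sided 90% exact upper limit is 1 − 0.05^(1/n). For n = 8 this is 0.31, but the table prints 0.37, which is the 95% value. If one row is at the wrong level, the whole table may be.

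Table 14 is the only place where either document states how precisely the primary safety proportion will be estimated. The zero-event rows tell a reader what toxicity rate could be excluded if no infant had an event. A label that disagrees with its numbers also leaves the intended level in doubt. If the setting that produced the table were carried into the final programs, intervals reported as 90% would in fact be 95%. That last point is a possibility only; nothing in the documents shows it will happen.

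**Working it through.** **Inputs.** All come from Protocol 8.7.1 and Table 14: n = 8, 12 and 20; the listed proportions; the Clopper-Pearson method; a labelled two-sided level of 90%. Each proportion times n is a whole number, so the event count x is never ambiguous: 0, 2, 4 of 8; 0, 3, 6 of 12; 0, 2, 4, 10 of 20.

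**Formula.** Lower limit = the α/2 quantile of Beta(x, n − x + 1), taken as 0 when x = 0. Upper limit = the 1 − α/2 quantile of Beta(x + 1, n − x). A 90% interval uses α = 0.10 and a 95% interval uses α = 0.05. For x = 0 the upper limit reduces to 1 − (α/2)^(1/n).

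**Hand check, 0 of 8.** At 95%: 1 − 0.025^(1/8) = 0.369. At 90%: 1 − 0.05^(1/8) = 0.312. Printed: 0.37.

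**All rows.**

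| x/n | Printed as 90% | Computed at 95% | Computed at 90% |
|---|---|---|---|
| 0/8 | (0.00, 0.37) | (0, 0.3694) | (0, 0.3123) |
| 2/8 | (0.03, 0.65) | (0.0319, 0.6509) | (0.0464, 0.5997) |
| 4/8 | (0.16, 0.84) | (0.1570, 0.8430) | (0.1929, 0.8071) |
| 0/12 | (0.00, 0.26) | (0, 0.2646) | (0, 0.2209) |
| 3/12 | (0.05, 0.57) | (0.0549, 0.5719) | (0.0719, 0.5273) |
| 6/12 | (0.21, 0.79) | (0.2109, 0.7891) | (0.2453, 0.7547) |
| 0/20 | (0.00, 0.17) | (0, 0.1684) | (0, 0.1391) |
| 2/20 | (0.01, 0.32) | (0.0123, 0.3170) | (0.0181, 0.2826) |
| 4/20 | (0.06, 0.44) | (0.0573, 0.4366) | (0.0714, 0.4010) |
| 10/20 | (0.27, 0.73) | (0.2720, 0.7280) | (0.3020, 0.6980) |

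Ten of ten rows reproduce at 95% and none at 90%. The 0.00 lower limits in the zero-event rows are the same at any level; the upper limits in those rows are still the 95% ones.

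**Tail check.** At the printed upper limits, the binomial probability of x or fewer events is between 0.023 and 0.027 in every row. That is 0.025 per tail apart from rounding. A 90% interval would give 0.05.

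**Other explanations tried.**
- A one-sided reading does not rescue the zero-event rows. The one-sided 95% upper bound is identical to the two-sided 90% limit (0.31, 0.22, 0.14), and the one-sided 90% bound is lower still (0.25, 0.17, 0.11).
- Wilson, Agresti-Coull, Jeffreys and Wald intervals, at 90% or 95%, do not reproduce the table. Agresti-Coull at 95% happens to give 0.37 for 0/8, for example, but gives (0.06, 0.60) for 2/8.

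**Size.** Zero-event upper limits, 95% over 90%:
- 0.3694/0.3123 = 1.18 for n = 8
- 0.2646/0.2209 = 1.20 for n = 12
- 0.1684/0.1391 = 1.21 for n = 20

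In the rows with events, the printed level gives intervals about 12% to 15% wider than planned. For 4/8 the widths are 0.6860 and 0.6142 (ratio 1.12); for 10/20 they are 0.4560 and 0.3960 (ratio 1.15).

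**The case against.** The arithmetic is not open to dispute; the case on the other side is about consequence.

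- **No decision uses Table 14.** Protocol 8.4 bases the sample size on the needs of the PK analysis. The suspension and pass/fail rules in Protocol 8.52 to 8.523 work on event counts and a 25% threshold, and their operating characteristics are in Tables 11 to 13. This stands.
- **The error is conservative.** The table understates precision, so nobody is falsely reassured. After 0 of 20, a reader is told that rates above 0.17 are excluded, when the planned interval would exclude rates above 0.14. The absolute gap with zero events is 0.03 to 0.06. This also stands.
- **The final report is protected.** The analysis itself is stated consistently as two-sided 90%, and SAP 4.6 requires code review, with double coding for the primary safety endpoint. A second programmer working from the SAP should catch a wrong level. This makes a mislabelled final interval unlikely, though it does not exclude one.
- **Two possible additions are optional.** Writing α = 0.10 into the SAP restates what a two-sided 90% interval already means. Extra rows at other group sizes would be an improvement and do not correct the error.

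These points limit the harm. They do not make the printed figures right.

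**Conclusion.** The concern holds. Every interval in Table 14 is a two-sided 95% Clopper-Pearson interval under a 90% label, so the stated precision of the primary safety analysis is wrong in all ten rows. The zero-event upper limits are 18% to 21% too high, and the remaining intervals are about 12% to 15% too wide. The result needs no assumption beyond the event counts, which the listed proportions fix exactly, and the method named in the footnote.

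The error is confined to the planning table and is conservative. The specified analysis, the safety guidelines and the sample size are unaffected. It should still be corrected, because this is the only precision statement for the primary safety endpoint and it contradicts its own label.

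**What to change.** Replace the ten intervals in Table 14 with the 90% limits:

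- n = 8: 0.00 (0.00, 0.31); 0.25 (0.05, 0.60); 0.50 (0.19, 0.81)
- n = 12: 0.00 (0.00, 0.22); 0.25 (0.07, 0.53); 0.50 (0.25, 0.75)
- n = 20: 0.00 (0.00, 0.14); 0.10 (0.02, 0.28); 0.20 (0.07, 0.40); 0.50 (0.30, 0.70)

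Since the protocol text, the table title, the column heading and the SAP all say 90%, recomputing is the natural correction. If 95% was intended, the table label, Protocol 8.7.1 and SAP 4.6 must all change together. That would alter the prespecified level of the primary analysis and is a larger amendment.

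Two optional additions:

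- State α = 0.10 in the programming specification for SAP 4.6, as a safeguard against the Table 14 setting being reused.
- Add rows at the sizes of the groups analysed separately under Protocol 8.7.1. SAP section 2 reports final accrual of 10, 6 and 26 mother-infant pairs. Assuming one infant per pair, each given at least one dose, the zero-event 90% upper limits are 1 − 0.05^(1/6) = 0.39, 1 − 0.05^(1/10) = 0.26 and 1 − 0.05^(1/26) = 0.11. The Cohort 2 RAL-exposed group, with a minimum of 8, is already covered by the n = 8 rows.

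The cost is one table correction and, if the safeguard is adopted, one line of SAP text. Trial conduct does not change.

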9.0 CLINICAL PHARMACOLOGY PLAN

Protocol exposure limits from non-compartmental analysis for each participant were $C_{max} \leq 8723.6$ ng/mL and $AUC_{12} \leq 28$ mg*h/L. A population PK model was developed incorporating cohort 1 PK data with RAL concentration data from 24 infants and children ages 4 weeks to < 2 years enrolled in IMPAACT P1066, a phase I/II, multicenter, open-label non-comparative intensive PK treatment study of RAL in infants and children [20]. Population modeling using PsN/3.7.6, NONMEM/7.3.0 and R/3.1.0 was performed to estimate RAL PK parameters, which were then used in simulations of potential dosing regimens. The regimen that best met PK exposure targets (C_{trough} , C_{max} , AUC) defined for safety and efficacy from studies in older infants, *children*, and adults was selected for evaluation Cohort 2 infants (RAL-exposed and RAL-naïve).

9.1 Pharmacology Objective

This study is designed to assess the pharmacokinetics of raltegravir in newborn infants. Based on pharmacokinetic data from IMPAACT P1097 and P1066, a starting dose of 3 mg/kg has been chosen, which is 25% of the total daily dose (6 mg/kg BID) currently under study in infants 4 weeks to <6 months of age in IMPAACT P1066. In Cohort 1 of the study, raltegravir will be administered as a single dose using 3 mg/kg of the oral granules for suspension within 48 hours of birth, and a second dose will be administered at 7 to 10 days of life.

PK evaluable infants are those whose PK results provide data on the primary pharmacokinetic parameters of interest.

The PK targets for Cohort 1 are:

- RAL concentrations in each individual that do not exceed a C_{max} of 19.63 μM and do not exceed an AUC₁₂ of 63.05 $\mu\text{M}\cdot\text{hr}$

Prior to the start of Cohort 2, the initially proposed dosing regimen was modified based on observed pharmacokinetic data, including data from the Cohort 1 RAL-naïve and RAL-exposed groups, coupled with modeling and simulation to determine the optimal multiple dosing regimen capable of meeting the selected PK targets, as well as the optimal PK sampling scheme for that dosing regimen.

Based on these data, in addition to standard of care ARV for PMTCT prophylaxis, Cohort 2 will receive the following dosing regimen (refer to tables in Appendix III):

- 1.5 mg/kg once daily during Days 1-7 of life (week 1)
- 3.0 mg/kg twice daily during Days 8-28 of life (weeks 2-4)
- 6.0 mg/kg twice daily during Days 29-42 of life (weeks 5-6)

The PK target AUC will depend on whether the drug is dosed once or twice daily. The PK target GM trough is the same for both once daily and twice daily dosing.

The PK targets for Cohort 2 are target exposures for:

- once-daily dosing of AUC₂₄ of 28-90 $\mu\text{M}\cdot\text{hr}$ (12-40 mgxh/L) and an approximate GM trough (C_{24hr}) > 75nM (33ng/mL)
- twice-daily dosing of AUC₁₂ of 14-45 $\mu\text{M}\cdot\text{hr}$ (6-20 mgxh/L) and an approximate GM trough (C_{12hr}) > 75nM (33ng/mL)

9.2 Primary and Secondary Data

The primary data to be collected are plasma raltegravir concentrations for pharmacokinetic parameter estimation. All PK samples will be registered in the Lab Data Management System (LDMS) database, and will be sent to the University of Alabama (UAB) Laboratory. The study database will be kept up to date by close tracking of samples. Intensive PK sample

assays and pharmacokinetic calculations will be performed on a regular basis in the UAB Laboratory so that ongoing interim analysis can be done by the protocol team.

9.3 Study Design, Modeling and Data Analysis

First dose and multiple dose raltegravir concentration-time data will be analyzed using standard non-compartmental methods. Whole blood for determination of raltegravir in plasma will be collected according to cohort. These sample collection times may change depending upon the ongoing analyses of the pharmacokinetic results.

Cohort 1

Pharmacokinetic sampling for infants in Cohort 1 included the following:

Dose 1 (within 48 hours of birth): Pre-dose, and 1-2 hours post-dose, 4-8 hours post-dose, 12 (± 1) hours post-dose, and 24 (± 1) hours post-dose.

Day 3-4 of life: One random PK sample will be obtained with laboratory evaluations.

Dose 2 (7-10 days of life): Pre-dose, and 1-2 hours post-dose and 24 (± 1) hours post-dose.

*Note: For the 12 and 24 hour PK sampling time points, it is necessary to collect blood samples within the window of ± 1 hour for the accurate calculations of PK parameters of raltegravir. However, in the event that a sample collection in this window is not possible, the sample should be obtained within ± 2 hours and this deviation from the sampling instructions should be recorded.

Modeling and simulation will be utilized after the completion of each RAL-exposed or RAL-naïve group in Cohort 1 to generate a multiple dosing scheme for the respective group in Cohort 2. Specifically, data may be integrated from P1110 Cohort 1, P1097, P1066 (Cohorts IV and V), P1026s, and adult oral granule data to construct a population PK model capable of describing the raltegravir pharmacokinetics of oral granules for suspension. A two-compartment model will be fit using NONMEM version VII software, where various population attributes including, but not limited to, age, weight, sex and creatinine clearance will be examined to determine their influence on the pharmacokinetics of raltegravir, including the absorption, bioavailability and clearance. Both intensive and sparse PK data from the above mentioned studies in both adults and children will be utilized to maximize the available information on the oral granules formulation and provide a rich and diverse dataset with regards to patient population, which should enable characterization of the population PK and associated variability for the oral granules for suspension formulation. By incorporating all available information regarding the evolution of raltegravir clearance and UGT1A1 ontogeny with age, the model can be used to simulate an optimal dosing scheme (with dose and/or frequency adjustments at appropriate times, such as at Day 14 and Day 28) to meet the PK targets throughout the course of dosing [76].

Cohort 2

Pharmacokinetic sampling for infants in Cohort 2 will occur at the Entry with first dose, after second dose, Day 6-9, Day 15-18, Day 28-32 visits, and Week 5-6 (33-42 Days of life) visit and include the following:

Note: PK sampling will ideally be scheduled after RAL has reached steady state (approximately 7-10 days after the dose increase). For example, the Day 15-18 PK sampling collection visit should ideally be scheduled 7-10 days after the infant received his/her RAL dose regimen increased from 1.5 mg/kg once daily to 3 mg/kg twice daily.

Entry with first dose: within 1 hour pre-dose, and 1-2 hours, 6-10 hours, 20-24 hours post-dose.

After second dose: PK sample obtained 3-6 hours post-dose with laboratory evaluations.

Day 6-9 of life: within 1 hour pre-dose of initiating 3mg/kg twice daily. A physical exam will also be conducted at this visit.

Day 15-18 of life: within 1 hour pre-dose, and 1-2 hours post-dose, 4-6 hours post-dose, and 8-12 hours post-dose.

Day 28-32 of life: within 1 hour pre-dose of initiating 6 mg/kg twice daily.

Week 5-6 of life (33-42 Days of life): within 1 hour pre-dose, and 3-6 hours post-dose.

For sparse PK samples, the time of the previously administered dose (unobserved dose) should be recorded.

9.4 Anticipated Outcomes

At the end of this trial we hope to have a much better understanding of raltegravir pharmacokinetics in neonates, the ontogeny of raltegravir metabolism, and to have defined the dose(s) and dosing interval that achieves the desired systemic exposure in this population.

10.0 HUMAN SUBJECTS

10.1 Institutional Review Board and Informed Consent

This protocol, the informed consent document (Appendix V-A and V-B), and any subsequent modifications must be reviewed and approved by the Institutional Review Board (IRB) or Ethics Committee (EC) responsible for oversight of the study. Written informed consent must be obtained from the parents or legal guardians of participants who cannot consent for themselves, such as those below the legal age. The informed consent will describe the purpose of the study, the procedures to be followed, and the risks and benefits of participation. A copy of the consent form will be given to the parent or legal guardian.

Each site which receives US HHS funding and follows the United States Code of Federal Regulations Title 45-Public Welfare, Part 46-Protection of Human Subjects (also known as the Common Rule) should have on record at the site a plan that detects and addresses any change in guardianship occurring in pediatric participants and determines when a study participant must have a consent process which involves a legally authorized representative (LAR) other than a family member with guardianship. The plan will include how the site determines when a LAR is initially or no longer needed and how frequently the LAR re-signs the consent. The plan should follow all IRB/EC, local, state, national and/or host country guidelines. Confirmation of such a plan at a site should be submitted with protocol registration materials.

10.2 Participant Confidentiality

All laboratory specimens, evaluation forms, reports, and other records will be identified only by a coded number to maintain participant confidentiality. All records will be kept in a secured area. All computer entry and networking programs will be done with coded numbers only. Clinical information will not be released without written permission of the participant, except as necessary for monitoring by the study staff, study monitors, drug companies supporting the study, and their designees, the OHRP, NIH, FDA, or the local IRB/EC.

10.3 Study Discontinuation

The study may be discontinued at any time by the IMPAACT network, the OHRP, NIH, FDA, or local IRB/EC, the pharmaceutical sponsors, or other governmental agencies as part of their duties to ensure that research participants are protected.

11.0 PUBLICATION OF RESEARCH FINDINGS

Publication of the results of this trial will be governed by IMPAACT policies. Any presentation, abstract, or manuscript will be made available for review by the pharmaceutical sponsors prior to submission.

12.0 BIOHAZARD CONTAINMENT

As the transmission of HIV and other blood borne pathogens can occur through contact with contaminated needles, blood, and blood products, appropriate blood and secretion precautions will be employed by all personnel in the drawing of blood and shipping and handling of all specimens for this study, as currently recommended by the Centers for Disease Control and Prevention. All infectious specimens will be sent using the ISS-1 SAF-T-PAK mandated by the International Air Transport Association Dangerous Goods Regulations-Packing Instruction 602. Refer to individual carrier guidelines (e.g., Federal Express or Airborne) for specific instructions.

APPENDIX I
MATERNAL SCHEDULE OF EVALUATIONS

	Screening ¹	Entry (V1.0 within 48 hours of delivery and V 2.0 within 60 hours of delivery) ¹	Labor and delivery ⁴
Informed Consent	X	(or) X	
CLINICAL EVALUATIONS			
History ²	X	(or) X	
HIV Test ³		6mL	
TOTAL BLOOD		6mL	

1. May be done at screening or at entry.
2. Obtain complete history including documentation of HIV-1 infection, demographic data, maternal antiretroviral dosing history, mode of delivery and obstetrical gestational age.
3. If maternal HIV status is unknown at the time of delivery, HIV testing is required as described in Section 4.11
4. The mother's participation in the study ends when she is discharged from the labor and delivery unit.

APPENDIX II-A

INFANT SCHEDULE OF EVALUATIONS FOR COHORT 1*

* Pharmacokinetic sampling collection times may be changed based on initial results from Cohort 1.

	Entry (within 48 hours of birth)	Dose 1 (within 48 hours of birth) Pre-dose	Dose 1 1-2 hours post-dose	Dose 1 4-8 hours post-dose	Dose 1 12 hours (±1hours) post-dose	Dose 1 24 hours (±1hours) post-dose	Day 3-4 of life	Dose 2 7- 10 days of life pre-dose	Dose 2 7-10 days of life 1-2 hours post-dose	Dose 2 7-10 days of life 24 hours (±1hours) post-dose	2 weeks of life (± 2 days)	6 weeks of life (±1 week)	24 weeks of life (±4 weeks)	Event Driven	Early Discontinuation
CLINICAL EVALUATIONS															
Informed consent	X														
History ¹	X						X	X			X	X	X		X
Physical exam	X ²						X ³	X ³			X ³	X ³	X ³		X ³
Pre-dose Monitoring ⁴							X	X							
Post-dose Monitoring ⁴										X			X		
LABORATORY EVALUATIONS¹²															
Hematology ⁵	0.5mL							0.5mL			0.5mL	0.5mL	0.5mL		
Chemistries ⁶	1mL						1mL ⁷	1mL			1mL	1mL	1mL		
VIROLOGY															
HIV nucleic acid test (HIV NAT) ⁸	3mL ⁹											3mL	3mL		
Resistance testing ¹⁰														2mL	
PHARMACOGENETICS¹⁶															
Genotyping ¹¹	250-400 µl														
PHARMACOKINETICS^{12,13,16}															
PK sampling		0.25mL	0.25mL	0.25mL	0.25mL ¹⁴	0.25mL ¹⁴	0.25mL ¹⁵	0.25mL	0.25mL	0.25mL ¹⁴					
TOTAL BLOOD	1.5-4.9mL	0.25mL	0.25mL	0.25mL	0.25mL	0.25mL	1.25mL	1.75mL	0.25mL	0.25mL	1.5mL	4.5mL	4.5mL	2mL	

APPENDIX II-A - FOOTNOTES FOR INFANT SCHEDULE OF EVALUATIONS FOR COHORT 1

1. History includes all non-protocol laboratory tests, HIV test results, antiretroviral agents (for PMTCT), concomitant medications, and any intercurrent illnesses since last visit.
2. Physical examination includes infant Apgar score, birth weight and length, gestational age, gender, and ethnicity.
3. Complete physical examination includes temperature, blood pressure, heart rate, respiratory rate, weight, length, and head circumference.
4. Pre and post-dose monitoring includes a telephone call by study staff to review medication instructions and check any side effects before and after PK sampling visits.
5. Hematology includes CBC with differential and platelet count which may be obtained any time on the first day of life.
6. Chemistries include AST, ALT, creatinine, and total and direct bilirubin which may be obtained any time on first day of life but must be obtained prior to enrollment of the infant.
7. Only total and direct bilirubin required.
8. HIV NAT may be either HIV RNA or HIV DNA. Collect 1-3mL depending on the type of platform performed at the site.
9. Obtain HIV NAT at entry if NOT done as part of standard of care.
10. Participants with confirmed vertical transmission should have 2mL of blood drawn for viral resistance testing to raltegravir and other ARVs as soon as possible after confirmation of HIV infection and should have safety assessments as described in Appendix II-C.
11. Genotyping (optional) for UGT1A1 and SLCO1B1 polymorphisms will be done using dried blood spot on filter paper. May be obtained with any blood sample.
12. Acceptable methods of blood collection for PK samples and laboratory evaluations are by venipuncture, heel stick or indwelling line.
13. When possible, an assessment of infant feeding (type and time of last infant feeding prior to RAL dose) should be recorded.
14. For 12 hour and 24 hour PK samples, window of ± 1 hour is necessary for the accurate calculations of the PK parameters of raltegravir. In the event that it is not possible to obtain sample within the ± 1 hour window, obtain within ± 2 hours.
15. Random PK sample.
16. See the Laboratory Processing Chart (LPC) on the P1110 Protocol Specific Webpage on the IMPAACT Website (<http://www.impactgroup.org>) for collection, processing and shipping instructions.

Priority of blood draw should be as follows:

- 1) Chemistries
- 2) Hematology
- 3) Pharmacokinetics

